#### *Sample Size*

According to Yong & Pearce (2013), EFA performs better with a larger sample size, as it reduces the error in the data. However, no formal sample size calculation is available for EFA, some authors recommend at least 200 participants (McCoach et al., 2013), while others put the targeted figure at 300 (Yong & Pearce, 2013). So, in this study, we are targeting a sample of 300 older adults and 300 informal caregivers. For the test-retest reliability, a sample size of 20

## **Development and validation of a health behaviour theory-based questionnaire to explore the willingness of older adults and informal caregivers to deprescribe (HBQtD)**

older adults, and 20 informal caregivers will be selected, as was used for rPATD validation (E. Reeve et al., 2016) and rPATD version for BZD (Péteïn et al., 2023).

As described earlier, this study will include an heterogeneous sample (recruitment will be carried out in various structures in Brussels and Wallonia ) to minimize the influence of variance and factor loading, which “give us an idea about how much the variable has contributed to the factor... they represent the strength of the correlation between the variable and the factor” (Kline, 1994 cit by Yong & Pearce, 2013).

### *Psychometric proprieties of the questionnaire*

The appropriateness of the data factor analysis, considered “to be a variable describing how much an individual would score on a factor” (Yong & Pearce, 2013), will be assessed using the Kaiser-Meyers-Olkin test and Bartlett’s test of sphericity. Factors will be extracted using the Principal Axis Factoring, that is based on the notion “that all variables belong to the first group and when the factor is extracted, a residual matrix is calculated. Factors are then extracted successively until there is a large enough of variance accounted for in the correlation matrix” (Tucker & MacCallum, 1997 cit by Yong & Pearce, 2013). In addition, for a better interpretation of the factors, a rotation will be performed, more precisely an oblique rotation (Yong & Pearce, 2013). The number of factors to be retained will be determined using the Kaiser-Guttman criterion (retaining all factors that are above the eigenvalue of 1) and the scree test (retaining all factors that are above the point of inflexion in the scree plot). Loadings above 0.30 will be considered as significant, as “anything lower would suggest a really weak relationship between the variables” (Tabachnic & Fidell, 2007 cit by Yong & Pearce, 2013).

Another essential step in the creation of a questionnaire is to gather evidence of the score's reliability (E. Reeve et al., 2016). In reality, score reliability “is an indication of the consistency, stability, or precision of scores” (McCoach et al., 2013). Consequently, reliability focus on two types of measurement: internal consistency that estimate a “measurement error within the set of questions” (McCoach et al., 2013) and test-retest reliability estimates, that is a measurement error across two or more instrument administration (McCoach et al., 2013).

The most commonly used estimated of internal consistency is Cronbach’s coefficient alpha ( $\alpha$ ; (McCoach et al., 2013)). Nevertheless,  $\alpha$  is predicted on several assumptions, that are not always respected (Trizano-Hermosilla & Alvarado, 2016; McCoach et al., 2013), which is why the omega coefficient ( $\omega$ ; (McDonald, 1999)) will also be used, as an alternative to  $\alpha$  (Doval, 2023; Trizano-Hermosilla & Alvarado, 2016). In reality, a number of researchers showed that  $\omega$  is a more sensible index, with lower risk of over- or underestimating reliability (Dunn et al., 2014). Therefore, the reliability coefficient range between 0 and 1, and a value above 0.7 will be considered as good internal consistency, while a value above 0.90 will be considered as excellent (Koo & Li, 2016).

According to Koo & Li (2016) “A more desirable measure of reliability should reflect both degree of correlation and agreement between measurements”, that’s why the intraclass correlation coefficient (ICC) will be used to evaluate test-retest reliability at the factor level, and linear-weighted Cohen’s Kappa and percent agreement at the individual item level. These measurements have been used to validate other instruments such as rPATD (E. Reeve et al., 2016) and the rPATD version for BZDs (Péteïn et al., 2023). The ICC classified the reliability

## **Development and validation of a health behaviour theory-based questionnaire to explore the willingness of older adults and informal caregivers to deprescribe (HBQtD)**

as poor (<0.50), moderate (0.50-0.75), good (0.75-0.90) and excellent (>0.90) (Koo & Li, 2016). The Cohen's Kappa nomenclature classify the strength of agreement also as poor (<0.00), slight (0.00-0.20), fair (0.21-0.40), moderate (0.41-0.60), substantial (0.61-0.80) and almost perfect (0.81-1.00) (Landis & Koch, 1977).

All numerical variables will be described using means, medians and standard deviation, whereas all categorical variables will be described using frequencies and proportion. A logistic regression analysis will be performed to better understand the association of items from the questionnaire and intention, or actual deprescribing behavior. The moderating influence of HL and locus of control on the effect of the determinants on deprescribing intention or behavior will be checked via moderation analysis using bootstrapping. Statistical analysis will be conducted using SPSS Statistics version 1.0.0.1406, and a type I error rate of <0.05 will be considered significant.

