**3. PROTOCOL SYNOPSIS**

Name of Sponsor UCLouvain (ARC, Actions de Recherche Concertée – Di-Prescribe)
Title of Study Development and validation of a health behavior theory-based questionnaire to examine the willingness of older adults and informal caregivers to deprescribe
Service(s) in which the experimentation is taking place Primary care setting, nursing homes in Brussels and Wallonia
Publication (reference)
Studied period : September 2023 to october 2024
Objectives: - Primary: to develop and validate a health behavior theory-based questionnaire to examine the older adults’ and informal caregivers’ determinants of deprescribing behavior - Secondary: assess the psychometric properties of this new instrument
Hypotheses The use of health behavioral constructs in the development of an assessment tool will have greater predictive validity than that of existing tools
Study Design Questionnaire development and validation that involve an item development and validation stage
Number of planned patients: - 345 older adults; 345 informal caregivers
Main criteria for inclusion (inclusion/exclusion criteria) Inclusion criteria: Older adult population: 
 
• Age 60 years or older;
 
• Taking at least 5 medications daily;
 
• Having at least one chronic condition;
 
 Informal caregiver (such as spouse, family/ friend caregivers): 
 
• Self-identified as a caregiver of an older adult who has 60 years old or older, that are taking at least 5 medications daily and having one or more chronic condition;
 
• The care recipient lived in the community or in a nursing home.
 
 Exclusion criteria: Older adult population: 
 
• Suffering from psychiatric trouble;
 
• Past or present drug or alcohol dependency;
 
• Having a terminal illness;
 
• Inability to complete a written questionnaire in French due to a functional or cognitive impairment;
 
• Inability to understand and express oneself in French.
 

**Development and validation of a health behaviour theory-based questionnaire to explore the willingness of older adults and informal caregivers to deprescribe (HBQtD)**

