
Informal caregiver population:
 

• Caregiver age under 18 years old;

• Caregivers who are paid for the care they provide;

• Caregiver inability to give consent and complete a written questionnaire in French;

• Caregiver inability to understand and speak in French.

Procedures: Schedule of assessments – Study Flowchart

Statistical Considerations
 
Methods that will be used to validate the questionnaire: face validity, content validity, construct validity, internal validity and test-retest reliability.
 
To assess the psychometric properties of the questionnaire, an exploratory factor analysis (EFA) will be performed – construct validity. Face and content validity will be performed by qualitative methodology, and using the content validity ratio (CVR). Internal validity will be assessed using the Cronbach’s alpha and omega coefficient, and test-retest reliability will be investigated using the Cohen’s kappa and Interclass correlation coefficient (ICC). Logistic regression will be performed to investigate the association between the determinants and the intention, or deprescribing behavior.

**Development and validation of a health behaviour theory-based questionnaire to explore the willingness of older adults and informal caregivers to deprescribe (HBQtD)**

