## **Development and validation of a health behaviour theory-based questionnaire to explore the willingness of older adults and informal caregivers to deprescribe (HBQtD)**

et al., 2016)), and Beliefs about Medicines Questionnaire (specific section) (BMQ-Specific) (Horne et al., 1999).

However, according to Turner et al. (2020) analyses, all 25 items found in the rPATD and BMQ-specific screening, only 8 were associated with deprescribing outcomes. In addition, these tools presents a low predictability validity for successful deprescribing (Chock et al., 2021; Turner et al., 2020), and an important gap between participants' intention and deprescribing behavior was also identified by Turner et al. (2020), with 86% of participants that are willing to deprescribe, but only 41% of participants successfully deprescribing their prescription. This significant gap and low predictive validity, can be explained by the fact that PATD and revised version was developed without a behavioral theory as a theoretical basis, whereas attitudes are a construct present in models of health behavior, such as the TPB (Ajzen & Madden, 1986). As a result, this questionnaire as well as the BMQ-specific questionnaires, do not take into account different critical domains that can be relevant to deprescribing, such as self-efficacy beliefs, outcome expectations, subjective norms, health goals, environmental barriers and enablers, among others (Linsky et al., 2015).

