### *Hypothesis*

According to Chock et al. (2021) and Turner et al. (2020) current tools, such as the BMQ and the widely used rPATD, have a number of limitations, particularly in terms of predictability validity for successful deprescribing. In addition, the rPATD items were developed without any theoretical basis in health behaviors, whereas attitudes are an important concept found, in particular, in the TPB (Ajzen & Madden, 1986). As a result, we hypothesis that the use of health behavioral constructs in the development of an assessment tool will have greater predictability validity on deprescribing behavior than that of existing tools.

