## **9. OBJECTIVES AND GOALS OF THE STUDY**

### *Primary objective:*

## **Development and validation of a health behaviour theory-based questionnaire to explore the willingness of older adults and informal caregivers to deprescribe (HBQtD)**

To develop and validate a health behavior theory-based questionnaire to examine the older adults' and informal caregivers' determinants of deprescribing intention or behavior (with separate version for older adult and informal caregiver).

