## **Development and validation of a health behaviour theory-based questionnaire to explore the willingness of older adults and informal caregivers to deprescribe (HBQtD)**

### *Method for data collection*

The questionnaire begins with a short introduction covering the importance of the study, its objectives, anonymity and the non-obligation to participate in the study and withdraw if desired. Consent will be signed before starting to fill in the questionnaire. The questionnaire initially asks 3 questions to determine participant eligibility, and the initial draft of the questionnaire consists of 3 main parts:

1. First section with questions relating to the socio-demographic and clinical characteristics of the participants. There are 5 basic demographic questions related to age, sex, education, relationship status, residence (at home, NH, ...). Three additional questions are included in this section to: (1) assess how the person feels about his or her health or that of the care recipient, on a Likert scale ranging from 1 “Poor” to 5 “Excellent”; (2) to know how many different medications (including those not prescribed by the doctor) the older person/care recipient takes per day; (3) to know if the person or the care recipient has ever tried, in the past, to reduce or stop some of the drugs in their usual treatment; (4) to know if the person/ informal caregiver are willing to deprescribe; (5) to know if the person/ care recipient is currently in the process of deprescribing at least one of the medication he or she is currently taking.
2. Second section with 58 questions for older adult questionnaire version and 55 questions for the informal caregiver version on factors that may be potential obstacles or facilitators to deprescribing behavior. Each item is rate on a Likert scale going from 1 “strongly disagree” to 5 “strongly agree”.

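### Does leaving the regression outcome as intention or behaviour make the association analysis unsound?

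*Combined protocol and SAP*

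**What the plan says.** Section 9.10.2 introduces the logistic regression as a way to understand "the association of items from the questionnaire and intention, or actual deprescribing behavior". The next sentence, on moderation by health literacy and locus of control, leaves its outcome open in the same way. The synopsis (Statistical Considerations) has "the association between the determinants and the intention, or deprescribing behavior".

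The stated targets differ in breadth. The primary objective in the synopsis is about "determinants of deprescribing behavior", while the one in section 9 covers intention or behaviour. The hypothesis in section 8 expects "greater predictability validity on deprescribing behavior than that of existing tools".

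Section 9.1 (Method for data collection) describes the variables. It says "Three additional questions are included in this section to" and then numbers five. Question 3 asks whether the person or care recipient "has ever tried, in the past, to reduce or stop some of the drugs in their usual treatment". Question 4 asks whether the person or informal caregiver is willing to deprescribe. Question 5 asks whether the person or care recipient is deprescribing at least one drug now. None of these is tied to the regression by number.

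**The concern.** A logistic model needs one defined binary outcome, and here a reader cannot point to it. Two of the three candidates could pass for actual behaviour. A past attempt (question 3) may also have shaped the beliefs now being measured, so a model of it could reverse cause and effect. In the caregiver version, moving from question 4 to question 5 also changes whose outcome is modelled.

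The protocol's own rationale separates the two constructs. Section 7 (Screening Tools) stresses a gap in an earlier study, "86% of participants that are willing to deprescribe, but only 41% of participants successfully deprescribing their prescription", and uses it to argue for a new tool. If *or* meant that either outcome could be chosen once the data were in, the list of determinants would depend on that choice. A willingness-only model would satisfy section 9.10.2 and leave behaviour unexamined.

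**Working it through.** **Plan's own figure.** The participant table in section 9.2 gives 5 + 10 + 30 + 300 = 345 per population, and the pre-test is 10% × 300 = 30. Both reproduce. The 300 comes from rules of thumb for exploratory factor analysis. No sample size, power or event count is given for the regression, so there is no regression figure to correct.

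**How different the outcomes could be.** Inputs: 86% willing and 41% successfully deprescribing (section 7, from another study), and n = 300 (section 9.10.2).

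- Minimum discordance, if everyone who deprescribes is willing: 0.86 − 0.41 = 0.45, and 0.45 × 300 = 135.
- Maximum phi: √[(0.41 × 0.14)/(0.59 × 0.86)] = √0.113 = 0.34.
- Assumed range of 70–86% willing and 10–41% deprescribing. At (0.70, 0.41): 0.29 × 300 = 87 and maximum phi 0.55. At (0.86, 0.10): 0.76 × 300 = 228 and maximum phi 0.13.

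**Precision.** SE of the log odds ratio per SD = 1/√[n·p·(1−p)]. Odds ratio detectable with 80% power (one predictor, two-sided 0.05) = exp(2.80 × SE).

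| Outcome | p | Smaller class of 300 | SE | Detectable OR per SD |
|---|---|---|---|---|
| Willing | 0.86 | 42 | 0.166 | 1.59 |
| Deprescribing | 0.41 | 123 | 0.117 | 1.39 |
| Deprescribing (assumed) | 0.10 | 30 | 0.192 | 1.71 |

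**Cost of choosing after the results.** With two independent outcomes, a null predictor reaches p < 0.05 on at least one with probability 1 − 0.95² = 0.0975, against 0.05. This applies only if one outcome is picked and the other is not reported. For scale, 58 draft items for older adults and 55 for caregivers, each tested at 0.05 with no true effect, would give 58 × 0.05 = 2.9 and 55 × 0.05 = 2.75 false positives on a single outcome. The analysis reads as description and not as a confirmatory test.

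**What the text lets an analyst infer.**

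1. *One model or two.* Section 9.1 (Study configuration) says that the systematic review behind the items sought theories explaining intention and/or behaviour. The questionnaire asks about both. Fitting both is the reading that uses what is collected.
2. *Which question is which.* Willingness is question 4. The word *actual* in section 9.10.2 fits current deprescribing (question 5) better than an attempt at any time in the past (question 3).
3. *Whose outcome.* The wording of each question already says: question 4 concerns the caregiver, and questions 3 and 5 the care recipient. Once the question is chosen, the subject is fixed.
4. *Objectives.* Intention or behaviour (section 9) contains behaviour (synopsis). This is a difference of scope and not a contradiction.
5. *Three against five.* This is a miscount in a sentence that then numbers every question. Section 15 lists both questionnaires as appendices, which would show what is asked and how it is answered.

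**The case for a change.** The strongest case for a change is that the regression and moderation analyses are the only planned ones linking the questionnaire to intention or behaviour, so they alone bear on determinants. Naming the outcomes would take a few sentences and no new data, and doing so before analysis would show that the choice did not follow the results.

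Part of this stands. The outcome is not named, the text gives no coding for questions 3 to 5, and nothing excludes question 3 as the behaviour measure. The constructs do differ, on the protocol's own account.

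The rest is weaker. The primary objective is to develop and validate an instrument, and the secondary objectives in section 9 are face and content validity and factor analysis. The regression serves understanding, and no conclusion about validity is made to depend on it. The hypothesis compares the new tool with existing ones, and naming an outcome would not supply that comparison. The numerical case is only illustrative: the 41% is successful deprescribing in another study, and neither a past attempt nor a current process measures success.

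There is also a possible circularity, since intention to deprescribe is among the dimensions behind the items. If intention items entered a model of willingness, their own associations would say little. The questionnaire is not in the text reviewed, so this cannot be checked, and an analyst would see the overlap on meeting it.

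**Conclusion.** No change follows. The plan leaves out a detail that a competent analyst would fill in one sensible way: model willingness (question 4) and current deprescribing (question 5) separately, in each version of the questionnaire, and report both. The moderation analysis would follow the same definitions. The discordance of at least 135 in 300 shows why the two should not be merged or swapped, but the plan does neither. The increase from 5% to about 10% in false positives for a null predictor would arise only under selective reporting, which the text does not call for.

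This rests on two assumptions: that *or* is read in line with the and/or in section 9.1, and that the regression stays descriptive. If the sponsor later used it as formal evidence of predictive validity for behaviour, the outcome and its coding would need to be fixed beforehand.

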### **9.11. Protocol Amendments**

If amendments to the protocol (modifying sense or objectives or modifying the study procedures) turn out to be necessary, they will be subjected at first opinion of the promoter of the study. After agreement by the promoter, these amendments will then be submitted to the opinion of the Ethic Committee having examined the initial protocol.

## **10. FINANCE AND INSURANCE**

This study is part of WP2 of the Di-Prescribe project, with ARC funding.

As part of this project, a budget has been set aside for stakeholder involvement. As it is planned to carry out FG with healthcare professionals, older adults and informal caregivers, a compensation of 50€ per person and per meeting will be granted. The budget also includes a travel allowance for participants. In addition to the involvement of stakeholders, a cost will be incurred for the purchase of stamps and envelopes for the return of paper questionnaires. This cost will be covered by the budget allocated for this purpose by ARC project.

The experimentation is covered under the Belgian Law of May 7, 2004 by a no-fault insurance (type of coverage: liability insurance).

Policy holder:

UCLouvain  
[name]  
[name]

Issuer of the certificate of insurance:

MS Amlin Insurance SE  
[name]  
[name]  
N° de police : LXX111372

# Development and validation of a health behaviour theory-based questionnaire to explore the willingness of older adults and informal caregivers to deprescribe (HBQtD)

## 11. END OF STUDY

The study end date is the date of the last returned questionnaire, which will be required to reach the sample size estimation. A maximum of one year is planned to complete this study, including recruitment, data collection, data analysis and preparation of the publication.

## 12. DISSEMINATION OF RESULTS AND PUBLICATION POLICY

The progress and results of this study will be discussed with the Di-Prescribe research team. The protocol and final results will be presented at seminars scheduled as part of the doctoral program. At the end of the study, a scientific publication will be written by the co-investigator ([name]) under the supervision of the sponsor representative and [name] [name]. A paper will also be written for publication in a peer-journal. Acknowledgements will be made to all those who will make this work possible, including healthcare professionals, the different institutions and organizations that will be contacted, as well as the older adults and informal caregivers who will take part in the study. In addition, some people who will be indirectly involved, in particular by giving support and guidance, will also be recognized.

## 13. ARCHIVING

At the end of the study, the paper data will be stored at the ‘Service des Archives’ from the UCLouvain for as long as dictated by local Ethical Committee and Institutional regulations. Data to be kept at least 20 years after the trial termination according to the Belgian legislation: RD 18 May 2006 art.24

